10.3.5. Pharmacokinetic/Pharmacodynamic Analyses

Open-label PK Lead-in (Study Period 2): Serial PK sampling will be conducted to confirm that the high doses in pediatric age cohorts will produce comparable exposure to the 4-mg dose in adults. Comparability will be assessed using non-compartmental methods (e.g., AUC and C_{\max}).

Double-blind Treatment (Study Period 3): All plasma baricitinib concentration–time data will be pooled and evaluated using population PK methods. A covariate screen of patient and study-specific factors will be included in the analyses based on factors investigated in previous

and (if any) ongoing PK analyses and on their relevance to the target population. Exploratory and/or model-based analyses examining the relationships between baricitinib exposure and efficacy and response endpoints will be conducted. Other analyses of efficacy and safety outcome measures may also be assessed as scientifically appropriate and warranted by available data. Details about the analyses to be conducted will be contained in the PK/PD analysis plan.

10.3.6. Evaluation of Immunological Measures

Patients who are immunized with TDaP or pneumococcal conjugate vaccines will have their IgG antibody titers to the antigens evaluated preimmunization and at 4 and 12 weeks postimmunization. A primary immune response will be assessed in patients who have never received TDaP or pneumococcal conjugate vaccines previously, and secondary/booster responses will be assessed if the patients have previously received the vaccines. More detailed analytical methods will be described in the SAP.

10.3.7. Other Analyses

10.3.7.1. Health Outcomes

The health outcome measures will be analyzed using methods described for continuous or categorical data as described for efficacy measures in Section 10.3.3.

10.3.7.2. Acceptability and Palatability

Responses from the tablet and suspension acceptability and palatability questionnaires will be summarized categorically (frequency and percentage) by age group, for each visit separately and in aggregate. In addition, general trends from baseline and Week 2 in acceptability and palatability will be analyzed.

10.3.7.3. Subgroup Analyses

To assess whether the treatment effect is similar across subgroups for the primary efficacy outcome, a logistic model will be used and will include treatment, stratification variables, the subgroup variable (e.g., age) and the subgroup by treatment interaction. If the interaction is statistically significant at $\alpha=0.10$, the nature of the interaction will be explored, that is, within each subgroup the treatment effect will be estimated. Similarly, for the continuous variable of EASI, the MMRM analysis will include additional variables for subgroup and the subgroup by treatment interaction.

Subgroups to be evaluated will include baseline disease severity, sex, age (<10 years or ≥ 10 years), race, prior therapy (intolerance or inadequate response to TCS/TCNI), other atopic conditions (e.g., food allergies, asthma, allergic rhinitis/rhinoconjunctivitis). Further definitions for the levels of the subgroup variables, the analysis methodology, and any additional subgroup analyses will be defined in the SAP. Because this study is not powered for subgroup analyses, all subgroup analyses (with the exception of age cohorts, which are adequately powered) will be treated as exploratory.

In the subgroup of older pediatric patients (10 to <18 years old), a frequentist approach will be used.

Younger Pediatric Patients (2 to <10 years old)

In the subgroup of younger pediatric patients (2 to <10 years old), a hierarchical Bayesian analysis will be conducted using a logistic regression analysis as described above. This logistic regression will also include covariate adjustments for disease severity (IGA) and treatment group in the model. The posterior probability and 95% credible interval (CrI) for the difference in proportion from the logistic regression model are used for primary statistical inference. Details of the Bayesian approach are described in the SAP.

The analysis of the younger pediatric patients will leverage results observed in older pediatric patients through a Bayesian approach for the primary efficacy outcome at 16 weeks. In this approach, the posterior distribution of the treatment response of baricitinib high dose in older pediatric patients will be used in the construction of a proper prior distribution for baricitinib high dose in younger pediatric patients which will be further described in the study JAIP SAP. A similar approach will be used for the baricitinib medium and low doses in younger pediatric patients given that these doses are expected to provide exposures that are similar to their corresponding doses in older pediatric patients. The statistical approach taken for the young pediatric patients is therefore grounded in (1) making best possible use of prospective patients' data through efficient analysis procedures and (2) formally evaluating and modelling these data in light of the broader scientific context provided by existing information from older pediatric patients regarding patient outcomes on both the treatment and placebo regimens. This is consistent with the EMA's Reflection paper on the use of extrapolation in the development of medicines for pediatrics. Furthermore, the methodology assures robust conclusions about efficacy of the investigational medicine in younger patients while ensuring the feasibility of the trial.

Additionally, a consistency check will be conducted to determine whether the response for a specific treatment arm in the younger pediatric populations is within the 95% CI observed in older pediatric patients. The planned sample size is 120 patients with 1:1:1:1 randomization. The planned sample size has >80% simulated power to detect any difference between the baricitinib high dose and placebo treatment groups or the baricitinib medium dose and placebo treatment groups with probability of at least 0.95 and that the observed effect is consistent with the effect seen in older pediatric patients. This calculation relies on the assumption that leveraging information from older patients in Study JAIP is warranted. If the consistency check is not satisfied, no information from the older cohort will be used. In the event that the subgroup of younger pediatric patients has slow patient accrual, this will become the primary analysis for the younger patient subgroup.

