10.1. Sample Size Determination

Approximately 25 patients will be enrolled into the Open-label PK Lead-in (Study Period 2) and may continue on open-label treatment during the long-term extension (Study Period 4). Data from patients participating in the PK lead-in will be analyzed separately from patients randomized into the Double-blind treatment (Study Period 3).

Study JAIP will aim to enroll at least 440 patients 2 to <18 years of age into the Double-blind Treatment period (Study Period 3), which includes at least 320 older pediatric patients (10 to <18 years) and at least 120 younger pediatric patients (2 to <10 years). The proposed sample size (N=440) will ensure a >95% power to detect any difference between the baricitinib high dose and placebo treatment groups or the baricitinib medium dose and placebo treatment groups, each using a 2-sided alpha of 0.05, assuming a 10% placebo, 25% medium dose, and 30% high dose response rate for the primary endpoint using a chi-squared test. The assumptions are based on what was observed in the Phase 2 study (JAHG). The proposed end point of IGA 0 or 1 represents patients whose AD is clear or almost clear from a baseline of moderate or severe disease. The anticipated effect size represents 3 times more patients achieving this benefit compared to placebo which, in discussion with therapeutic experts, is of a magnitude that is considered to be clinically relevant.

Furthermore, in older pediatric patients the sample size of 320 is sufficient to detect that the baricitinib high or medium dose is superior to placebo at least 80% of the time. Similarly, in the younger pediatric patients, the planned sample size of 120 patients has > 80% simulated power using the Bayesian approach described in Section 10.3.7.3 and in the Study JAIP SAP to detect any difference between the baricitinib high dose or medium dose and placebo treatment groups with a probability threshold of 0.95.

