10.3. Statistical Analyses

10.3.1. General Statistical Considerations

Statistical analysis of this study will be the responsibility of Lilly or its designee. A detailed SAP describing the statistical methodologies will be developed by Lilly or its designee.

Any change to the data analysis methods described in the protocol will require an amendment ONLY if it changes a principal feature of the protocol. Any other change to the data analysis methods described in the protocol, and the justification for making the change, will be described in the clinical study report (CSR). Additional exploratory analyses of the data will be conducted as deemed appropriate.

All tests of treatment effects will be conducted at a 2-sided alpha level of 0.05, unless otherwise stated (e.g., refer to Section 10.3.7.3). Treatment comparisons of discrete efficacy variables between baricitinib and placebo will be made using a logistic regression analysis with region, disease severity, age, treatment group, and treatment group-by-age interaction in the model. The percentages, difference in percentages, and 95% confidence interval (CI) of the difference in percentages will be reported. Treatment-by-age interaction will be added to the logistic regression model of the primary and key secondary variables as a sensitivity analysis. If this interaction is significant at a 2-sided 0.1 level, further inspection will be used to assess whether the interaction is quantitative (i.e., the treatment effect is consistent in direction but not size of effect) or qualitative (the treatment is beneficial for some but not all age groups). The p-value from the Fisher exact test will also be produced.

When evaluating continuous measures over time, a restricted maximum likelihood-based mixed-effects model of repeated measures (MMRM) will be used. The model will include treatment, age cohort, baseline severity, visit, and treatment-by-visit interaction, and treatment-by-age cohort interaction as fixed categorical effects and baseline score and baseline score-by-visit interaction as fixed continuous effects. Region may be included in the model if

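### For the exploratory non-age subgroups, Section 10.3.7.3 ties within-subgroup effect estimates to an interaction p-value below 0.10, a gate that is weak at this sample size and selects exaggerated differences

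*Protocol*

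**What the plan says.** Protocol Section 10.3.7.3 gives the aim: "To assess whether the treatment effect is similar across subgroups for the primary efficacy outcome". The tool is a logistic model with treatment, the stratification variables, the subgroup variable and their interaction. The rule applies when that interaction reaches significance at 0.10: "the nature of the interaction will be explored, that is, within each subgroup the treatment effect will be estimated". The listed subgroups are baseline severity, sex, age, race, prior therapy and other atopic conditions.

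The same section says the study is not powered for subgroup analyses and treats all except the age cohorts as exploratory. It leaves subgroup levels, methodology and additional subgroup analyses to the SAP. The two age cohorts have their own analyses there: frequentist for patients aged 10 and over, Bayesian with a 95% credible interval for those under 10. Neither depends on an interaction test.

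For EASI, the section adds subgroup and interaction terms to the MMRM without restating the 0.10 condition.

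**The concern.** The stated question is whether effects are similar. A test of difference, with no margin and no required interval, cannot answer it when the test has little power. As written, the subgroup effects are to be estimated only when that test succeeds. This has two consequences.

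- A subgroup in which the drug does little or nothing will often not trigger the estimate that would show it.
- The estimates that do appear have been selected for looking different, so they are biased away from each other.

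The primary test, alpha, dose selection and stopping are untouched. What is at stake is what a reader can learn about severity, sex, race, prior therapy and atopic comorbidity.

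**Working it through.** **Inputs from the protocol.** 110 patients per arm (Section 5.1). Response rates: "assuming a 10% placebo, 25% medium dose, and 30% high dose response rate for the primary endpoint using a chi-squared test" (Section 10.1). Gate at 0.10 (Section 10.3.7.3), taken as 2-sided because Section 10.3.1 uses a 2-sided 0.1 level for its age interaction.

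**Assumptions.** The protocol gives no subgroup sizes for the non-age factors, so I use an even split (55/55 per arm) and an 80/20 split (88/22 per arm). One subgroup, A, has the planning rates. The other, B, has 10% on drug and on placebo. Stratification covariates are left out.

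**The plan's own figure.** The protocol states power above 95% for the dose comparisons and none for the interaction. The two-proportion chi-squared calculation at 110 per arm, 2-sided 0.05, gives 96.4% for high dose versus placebo and 83.8% for medium dose versus placebo. By simulation, the chance that at least one of the two is significant is 98.3%. The stated figure thus reproduces for the high dose and for the either-dose reading, but not for the medium dose alone. That is a separate matter.

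**Formula for the gate.** d = difference between the two log odds ratios. SE = square root of the sum of 1/(n·p·(1−p)) over the four cells. Power = Φ(d/SE − 1.645) + Φ(−d/SE − 1.645).

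**High dose, even split.**
- d = logit(0.30) − logit(0.10) = −0.847 + 2.197 = 1.350, because the log odds ratio in B is 0.
- SE² = 3/(55·0.09) + 1/(55·0.21) = 0.606 + 0.087 = 0.693, so SE = 0.832.
- d/SE = 1.622, power 49%, gate closed in 51%.

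**High dose, 80/20 split (no-effect subgroup is the 20%).**
- SE² = 1/(88·0.09) + 1/(88·0.21) + 2/(22·0.09) = 0.126 + 0.054 + 1.010 = 1.190, so SE = 1.091.
- d/SE = 1.237, power 34%, gate closed in 66%.

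All scenarios, with a likelihood-ratio simulation as cross-check:

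| Comparison | Split | Closed, Wald | Closed, likelihood ratio |
|---|---|---|---|
| High dose, 30% in A | even | 51% | 49-50% |
| High dose, 30% in A | 80/20 | 66% | 64% |
| Medium dose, 25% in A | even | 63% | 61% |
| Medium dose, 25% in A | 80/20 | 74% | 71% |
| High dose, 50% in A | even | 15% | 17-18% |

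The last row keeps the overall high-dose rate at the planned 30%: (50% + 10%)/2. There d = 2.197, SE = 0.824 and d/SE = 2.67.

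**Selection effect** (20,000 simulated trials per setting, high dose, likelihood-ratio gate).
- Even split, true differences of 20 points in A (10% versus 30%) and 10 points in B (10% versus 20%). The gate opens in 19% of trials. In those, the gap between subgroups averages 21 points against a true 10, and the weaker subgroup averages 4 points instead of 10.
- No true interaction (10% versus 30% in both). The gate opens in 11% of trials for the even split and 13% for 80/20, with average absolute gaps of 19 and 21 points. For comparison, the gap over all even-split trials has SD √(2·(0.09 + 0.21)/55) = 10.4 points, so its average absolute size is about 0.80 × 10.4 = 8 points.

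**What ungated reporting would show.** For a true null effect at 10%, a typical 95% CI for the odds ratio is 0.29 to 3.5 with 55 per arm and 0.14 to 7.2 with 22 per arm. On the difference scale the half-widths are 1.96·√(2·0.09/55) = 11 points and 1.96·√(2·0.09/22) = 18 points.

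**The case against.** **The analyses are exploratory, and the protocol says so.** This is true and lowers the stakes: nothing confirmatory rests on these subgroups. It does not defend the gate. An analysis declared unpowered is better reported as estimates with intervals than switched on by an underpowered p-value.

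**Methodology is left to the SAP.** The SAP may well tabulate every subgroup level. A reader might infer that estimates are otherwise withheld or forbidden. The text does not go that far: it states when effects will be estimated and does not rule out further output. But the condition is written in the protocol, and the general deferral does not remove it.

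**Non-significance is nowhere called similarity.** This is correct. A reader might infer that a non-significant result will be taken as similar, since similarity is the declared aim and the interaction test the only stated criterion. No passage says so.

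**Age.** A reader might extend the point to age, or to the rule in Section 10.3.1 that "If this interaction is significant at a 2-sided 0.1 level, further inspection will be used". The documents do not support that. Both age cohorts are estimated without a gate (Sections 10.3.7.3 and 10.3.8), and the Section 10.3.1 trigger leads only to closer inspection of a sensitivity analysis.

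**The size depends on the scenario.** This stands. Putting the planning rates in one subgroup and no effect in the other lowers the overall high-dose rate to 20% for an even split. Keeping it at 30% cuts the closed-gate rate to about 15-18%. A single headline percentage without its assumptions would mislead.

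**Conclusion.** The point holds for the non-age subgroups. Their within-subgroup effects have one stated route, an interaction significant at 0.10. At 110 per arm, that gate stays closed in about 50% (even split) to 65% (80/20 split) of trials for high dose versus placebo when the drug does nothing in one subgroup and has its planned 10% versus 30% in the other. This rests on assumed subgroup shares and a 2-sided test without covariates. The range is about 61-74% for the medium dose and about 15-18% if the responsive half reached 50%. When the gate opens, the displayed differences are inflated, roughly doubled in the 20-versus-10-point example. This is a reporting rule worth correcting in exploratory analyses, with no bearing on the primary conclusion.

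**What to change.** In Section 10.3.7.3, delete the 0.10 condition for the non-age subgroups. State instead that:

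- the treatment difference versus placebo, with its 95% CI, is reported at every prespecified subgroup level whatever the interaction p-value;
- the interaction p-value is given descriptively;
- a non-significant interaction is not read as evidence of similarity;
- these analyses remain exploratory.

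No change is needed to the age-cohort analyses or to Section 10.3.1. The cost is a wording change and a table or forest plot. No extra data are needed, and the primary test and alpha are unaffected. The downside is a few more exploratory estimates with wide intervals, and those intervals show how little the trial can say about small subgroups.

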10.3.8. Interim Analyses

No interim analyses are planned for this study. The analysis of Study Period 3 data is considered to be the primary analysis. If an unplanned interim analysis is deemed necessary, the appropriate Lilly medical director, or designee, will be consulted to determine whether it is necessary to amend the protocol. Additional analyses in order to support regulatory submission may be required after patients have completed the primary endpoint during Study Period 3, and these additional analyses will be specified in the SAP.

In the event that the older subgroup of patients (10 to <18 years old) completes the Double-blind Treatment period (Study Period 3) more than 6 months earlier than the anticipated completion date for the younger subgroup of patients (2 to <10 years old), each age subgroup is adequately powered and can be individually unblinded and analyzed according to a pre-planned analytical approach. In this pre-planned approach, the older subgroup of patients will be locked and analyzed (using a frequentist approach) after all patients in the subgroup have completed or discontinued from Study Period 3, and this analysis will be considered the primary analysis for the older subgroup. Subsequently, after all patients in the younger subgroup have completed or discontinued from Study Period 3, the data from the younger subgroup will be locked and analyzed (using a Bayesian approach), and this analysis will be considered the primary analysis for the younger age subgroup. The database lock and analysis of the data from the older subgroup of patients will not be considered an interim analysis and no alpha will be spent because the analysis of each age subgroup will be conducted independently and will be considered the primary analysis for the age group. In this situation, the combined analysis of the entire study population (2 to <18 years old) will be considered a secondary analysis. Further details of this pre-planned analytical approach will be included in the study JAIP SAP.

10.3.8.1. Data Monitoring Committee

A DMC will monitor the overall safety of this trial. The DMC will consist of members external to Lilly. This DMC will follow the rules defined in the DMC charter, focusing on potential and identified risks for this molecule and for this class of compounds. Data Monitoring Committee membership will include, at a minimum, specialists with expertise in pediatrics, statistics, and other appropriate specialties.

The DMC will be authorized to review unblinded results of analyses by treatment group prior to database lock, including study discontinuation data, AEs including SAEs, clinical laboratory data, vital sign and growth data, etc. The DMC may recommend continuation of the study as designed; temporary suspension of enrollment; or the discontinuation of a particular age cohort, dose regimen or the entire study. While the DMC may request to review efficacy data to investigate the benefit/risk relationship in the context of safety observations for ongoing patients in the study, no information regarding efficacy will be communicated. Moreover, the study will not be stopped for positive efficacy results nor will it be stopped for futility. Hence, no alpha is spent. Details of the DMC, including its operating characteristics, will be documented in a DMC charter and DMC analysis plan.

Besides DMC members, a limited number of pre-identified individuals may gain access to the limited unblinded data from Study Period 3, as specified in the unblinding plan, prior to the database lock for the primary analysis or final database lock to initiate the final population PK/PD model development processes or for preparation of regulatory documents, respectively. Information that may unblind the study during the analyses will not be reported to study sites or the blinded study team until the study has completed.

Unblinding details will be specified in a separate unblinding plan document.

10.3.8.2. Adjudication Committee

A blinded external Clinical Event Committee will adjudicate potential MACE (cardiovascular death, myocardial infarction [MI], stroke), other cardiovascular events (such as hospitalization for unstable angina, hospitalization for heart failure, serious arrhythmia, resuscitated sudden death, cardiogenic shock, coronary revascularization such as coronary artery bypass graft or percutaneous coronary intervention), venous and arterial thrombotic events, and noncardiovascular deaths. Details of membership, operations, recommendations from the Committee, and the communication plan will be documented in the Charter.

10.3.8.3. Unblinded Study Team for Regulatory Submission

For the purpose of regulatory submission, a limited number of pre-identified individuals will have access to unblinded efficacy data when all the patients complete Week 16 assessments; hence, a portion of the long-term assessments may be unblinded prior to the final database lock. Only the blinded study team will communicate with sites on regular trial conduct issues, and study sites will not receive any efficacy and safety information on an individual patient level from this early analysis for regulatory submission.

Besides DMC members and the Unblinded Study Team for Regulatory Submission, a limited number of pre-identified individuals may gain access to the limited unblinded data, as specified in the unblinding plan, prior to the final database lock for preparation of regulatory documents. Information that may unblind the study during the analyses will not be reported to study sites or the blinded study team until the study has completed.

Unblinding details will be specified in a separate unblinding plan document to ensure proper firewalls between the unblinded study team and the blinded study team and study sites.

11. References

